### **Compilation and presentation:**

- After the interim analysis, the data will be compiled, and the manuscript will be ready for peer review, estimated for 2026–2027.
- After the local study's completion, the data are compiled and the manuscript is ready for peer review, estimated for 2029.
- After the national multicenter study, data are compiled, and the manuscript is ready for peer review, estimated for 2033.

### **3.4 Study Registration**

Both the local pilot study and the national multicenter study will be registered on ClinicalTrials.gov or equivalent registry.

### **3.5 Power Analysis**

Calculating the statistical power of the study is associated with significant uncertainty. The first local study is hypothesis-generating and motivates a subsequent national multicenter study for validation. An approximate calculation gives an estimated sample size of approximately 250 examinations.

#### Project's Specific Question

- Can computed tomography angiography replace four-vessel angiography as a supplementary radiological examination to determine total brain infarction within the Swedish legal framework?
- How is a new CT-Angiography-based protocol interpreted in comparison with four-vessel angiography, where there is a need for radiological confirmation of ceased circulation to the brain?

### **3.6 Method**

#### **Patient Recruitment**

Recruitment of research subjects occurs in connection with the decision or execution of clinical diagnostics with direct criteria. After two consecutive clinical neurological examinations with at least two hours in between, where the clinically responsible physician has not been able to demonstrate remaining cranial nerve functions or spontaneous breathing, a suspicion is formed according to clinical practice that complete brain infarction is present, and a decision on four-vessel angiography is made.

- Patient undergoes transcranial Doppler (TCD) to assess the flow profile or its absence. The examination takes approximately 10 minutes. Images/data/results are blinded for the responsible neuroradiologist.
- Research subjects are randomized to undergo computed tomography before or after four-vessel angiography and are examined in the order specified by randomization.
- Images/data/results of computed tomography examination are blinded for the responsible neuroradiologist to avoid bias. The computed tomography examination is performed on one occasion; the time required is approximately 5 to 10 minutes, including transfer from bed to stretcher to bed.
- Research subject undergoes two consecutive four-vessel angiographic examinations performed by a neuroradiologist, with at least 30 minutes between them.

- A trained interventional neuroradiology (INR) operator confirms or denies ceased circulation to the brain's vessels based on four-vessel angiography.
- In the event of a cessation of cerebral circulation, death is documented with date and time, in accordance with clinical practice.
- Research subject returns to the intensive care unit.

### **Collected Research Data:**

#### **eCRF:**

- Patient data, demographic variables, injury mechanism and date, execution date and time for clinical neurological examination (see eCRF below). Cardiopulmonary physiological data.
- Kidney function parameters include fluid balance, creatinine, urea, estimated glomerular filtration rate, and electrolytes.

### **Computed Tomography Angiography:**

- According to a prespecified examination protocol.
- Four consecutive computed tomography examinations from cervical vertebra 2 to the skull's vertex, of which the first examination is without contrast for reference and the following three examinations constitutes a multiphase examination of the same contrast bolus.
- Subsequent examinations according to calculations for time regarding contrast propagation in relation to time point 0 which is defined as when a sufficient amount of contrast reaches a specific measurement point in the aortic arch.
- Image sequences are clearly marked with respect to time relative to T=0.
- Standardized contrast medium volume is administered (according to clinical practice) with a minimum of 5 ml/second via power injector.
- Image sequences are acquired with the lowest possible slice thickness and at the lowest possible tube current. Tube currents above 100 kV are not allowed to increase the iodine sensitivity.
- Images are saved locally in the Karolinska Picture Archiving and Communication System (PACS).

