## 2 Background

Total brain infarction, which is equivalent to human death, is confirmed after a two-step clinical neurological exam. This exam assesses cranial nerve functions and the individual's ability to breathe independently. In some instances, it is necessary to verify this diagnosis with a radiological method to confirm that total brain infarction has occurred. Such situations include when brain function is affected metabolically or pharmacologically, when body temperature is too low, when the cause of total brain infarction is unclear, or when injuries to the brainstem or posterior cranial fossa make clinical diagnosis difficult. Additional cases include situations where the clinical exam is incomplete, such as in cases of high spinal injury, facial injury, severe chronic obstructive pulmonary disease, chronic hypoxia, or pacemaker dependency.

In summary, a significant proportion of clinical neurological examinations need to be supplemented with a radiological examination to determine total brain infarction and establish conditions for so-called DBD donation – donation after brain death (donation after injury that has given rise to brain death). The gold standard for such radiology in Sweden is aortocranial angiography, or four-vessel angiography, a catheter-guided injection of contrast medium to demonstrate the absence of blood flow to the brain's vessels.

Four-vessel angiography can mainly be performed at regional and university hospitals by a radiologist with neuro- or vascular intervention competence and is a resource-intensive procedure. The lack of equipment and necessary competence at smaller hospitals poses challenges for performing the examination locally. Today, four-vessel angiography has essentially no indication other than determining total brain infarction, which is why the method is not part of every radiologist's competence or every hospital's routine examination.

If a patient with probable arrested circulation to the brain needs to be transported to another hospital for such an examination, difficult emotional decisions sometimes arise for next of kin and ethical decisions for healthcare providers. It also places great logistical demands on healthcare and risks constituting an obstacle to a donation process.

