A significant proportion of these patients are potential organ donors, for whom medical principles and national legislation place particularly high demands on diagnostic reliability. Furthermore, there is a need to make diagnostic methods available outside regional and university hospitals where specialized neuroradiological competence may be lacking. Against this background, SBU (Swedish Agency for Health Technology Assessment and Assessment of Social Services) investigated in 2018 the scientific basis for assessing the reliability of two alternative diagnostic methods to four-vessel angiography: CT-Angiography and dMRI. The summary conclusion of the report was that CT-Angiography was still a method under development, that there were insufficient studies with a desirable and direct comparison between four-vessel angiography and CT-Angiography, and that there were too few studies with dMRI to make an assessment (9).

The difficulties presented were that many studies included in the report used clinically established brain infarction as a reference standard for comparison with CT-Angiography, meaning that the specificity of CT-Angiography could not be assessed. Furthermore, in several patients the clinical neurological examination was inconclusive, and objections were raised that there were no consensus or clear protocols for how the examination should be applied. On behalf of the Swedish National Donation Centre, SBU produced documentation on diagnostic reliability for nuclear medicine methods for determining total brain infarction. It was stated that the diagnostic reliability of gamma camera examination with Technetium was the same as that of four-vessel angiography in adults and children over two years and constituted an acceptable substitute (10). However, we note that nuclear medicine techniques cannot compete with CT-Angiography in terms of availability, should such a practice be enabled.

The question of whether a CT protocol could replace four-vessel angiography is thus not new but has not been studied in a way that would allow the question to be clearly addressed. The main advantages of applying CT-Angiography for this purpose, in addition to increased

availability, are that the method has a very high degree of sensitivity to intravascular contrast and that robust, operator-independent protocols can be developed and distributed.

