### **Conventional Four-Vessel Angiography:**

- Two consecutive four-vessel angiographies are performed with at least 30 minutes in between.
- Images are saved locally in the Karolinska Picture Archiving and Communication System (PACS).
- Date and time for established outcome (positive or negative examination).

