### **Processing of Computed Tomography Angiography:**

- The validity of the X-ray examination is tested by reviewing the entire series and confirming that it meets the requirements for contrast filling of extracranial vessels.
- Two board certified neuroradiologists will conduct an initial training session determining allowed contrast filling over the phases.

- Following a washout period of a minimum of two weeks, the neuroradiologists will independently re-review all images and determine a binary outcome of cessation of blood flow compatible with brain death in the same manner as the four vessel angiography is evaluated.
- After an additional wash out period of a minimum of four weeks the images will be independently re-reviewed.
- Following the two reading sessions inter- and intrarater agreements will be determined and comparison to gold standard test will be performed.

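### Does contrast left over from the angiographies compromise the CT readings in subjects randomised to CT after angiography?

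*Protocol*

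**What the plan says.** All references are to the protocol.

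- **Order.** Section 3.6, Patient Recruitment: "Research subjects are randomized to undergo computed tomography before or after four-vessel angiography and are examined in the order specified by randomization". The allocation ratio is not stated.
- **Reference test.** Section 2 describes four-vessel angiography as "a catheter-guided injection of contrast medium". Section 3.6, Conventional Four-Vessel Angiography: "Two consecutive four-vessel angiographies are performed with at least 30 minutes in between".
- **CT acquisition.** Section 3.6, Computed Tomography Angiography, has CT done "According to a prespecified examination protocol". There are four scans, "of which the first examination is without contrast for reference"; the other three follow a single bolus. Images are kept in the hospital archive.
- **CT reading.** Section 3.6, Processing, tests validity by "reviewing the entire series and confirming that it meets the requirements for contrast filling of extracranial vessels". Two neuroradiologists hold "an initial training session determining allowed contrast filling over the phases", then read all images independently in two sessions.
- **Times.** Section 3.6, Timestamps, records the time of CT and the start and end of angiography.
- **Analysis.** Sections 3.6 and 3.10 name sensitivity, specificity, predictive values and rater agreement, in summary form.

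**The concern.** A subject allocated to CT second may already have received contrast from two angiographies. CT is then read for intracranial contrast, and Section 2 itself says of CT angiography that "the method has a very high degree of sensitivity to intravascular contrast". If earlier contrast were still visible, the first scan would not be a clean baseline, and leftover contrast might be taken for filling. The most obvious result would be a lower apparent sensitivity in the CT-second group.

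The scientific question is whether CT can replace angiography, so in the intended use no angiography comes first. Only the CT-first subjects are examined under that condition. A single pooled accuracy figure could not show whether the CT-second readings were affected. The stated validity criterion concerns extracranial filling, and the training step concerns filling across the phases. Neither mentions contrast present before the bolus.

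**Working it through.** The protocol states no figure on this point, so there is none to reproduce. The check has two parts.

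**1. The text side by side**

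- *Is the statement about the first scan wrong?* No. It describes a scan taken before the CT bolus, and that holds in either order. It does not claim that the subject has never received contrast.
- *Is pooling over the two orders wrong?* No. Order is assigned at random, so the groups are comparable on average and the pooled result is a valid average over the two orders. A fixed order would have a drawback of its own: any change in circulation between the tests would always run in the same direction.
- *Is the information lost?* No. Four elements are already in place: a pre-bolus scan, its storage, the randomised order, and times from which the angiography-to-CT interval can be derived for each subject. Residual contrast can be assessed from these without new data.
- *What is absent?* A stated interval, a yes/no reader item, and a display of accuracy by order. The last is commonly left to the statistical analysis plan. The first two could sit in the CT examination protocol or the reader form, which are not shown.

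**2. What the numbers can and cannot say**

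Inputs: about 50 local patients and 200 additional patients in the national study (Section 3.3). Assumed, because the protocol does not give them: 1:1 allocation, hence 25 and 100 subjects with CT second, and all subjects positive on the reference test.

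- Exact 95% upper limit when no pre-bolus scan shows contrast, 1 − 0.025^(1/n): 13.7% for 0 of 25 and 3.6% for 0 of 100.
- If a share f of CT-second readings flipped, pooled sensitivity would move by f/2. At those limits this is 13.7/2 = 6.9 points and 3.6/2 = 1.8 points. These are halves of confidence limits, not maxima, and they assume that every affected scan is recognised.
- Chance of seeing at least one affected subject among 25, 1 − (1 − f)^25: 0.72, 0.93 and 0.996 for assumed f of 5%, 10% and 20%.
- Precision by order (Clopper-Pearson): 21/25 gives 0.64 to 0.95, against 0.71 to 0.93 for 42/50 pooled. With three reference-negative subjects in one order, 3/3 gives 0.29 to 1.00.
- Power of Fisher's test, two-sided 0.05, for 90% against 70%: 0.305 with 25 per order and 0.935 with 100 per order.

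These results describe what an extra check could detect. None measures a defect, because the true f is unknown and may be zero. They also show that a by-order comparison in the local study would settle little.

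**The case for a change.** The strongest case for the concern is that nothing shown obliges anyone to look at the pre-bolus scan for residual contrast, and that a check improvised after the results are known is weaker than one defined beforehand. Randomisation makes the two orders comparable, but it does not make CT after angiography the same as stand-alone CT. Section 2 also reports that a direct comparison with angiography put low CT sensitivity down to stasis filling, so misread contrast is a real issue in this field. In addition, Section 3.3 plans an interim analysis after about eight subjects to choose which image sequences to keep, and no text protects the pre-bolus scan.

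The factual part stands: no interval and no such item are stated. A reader item and a descriptive by-order table would be reasonable additions. They remain optional detail. Section 3.3 does not say that the pre-bolus scan may be dropped. The item is not free of cost either: completed after the first reading session, it could alert readers to the examination order before the second and so disturb the planned intrarater comparison. Neither addition would change how CT is read or the pooled accuracy result.

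**Conclusion.** The concern does not hold. The protocol states nothing false about the first scan, does not contradict itself, and makes no invalid choice in randomising the order and pooling over it. The omissions are matters of detail that the statistical analysis plan or the separate examination protocol may cover, and the data needed to examine the question are already collected. The local study is described as hypothesis-generating (Section 3.5), and a second phase follows it.

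No size can be attached to the effect from the document. The 6.9-point and 1.8-point figures depend on 1:1 allocation, on all subjects being reference-positive, on zero observed cases, and on every affected scan being recognised. The conclusion assumes that the pre-bolus scan continues to be acquired and stored as Section 3.6 describes.

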### **Conventional Four-Vessel Angiography:**

- Two consecutive four-vessel angiographies are performed with at least 30 minutes in between.
- Images are saved locally in the Karolinska Picture Archiving and Communication System (PACS).
- Date and time for established outcome (positive or negative examination).

### **Processing of Computed Tomography Angiography:**

- The validity of the X-ray examination is tested by reviewing the entire series and confirming that it meets the requirements for contrast filling of extracranial vessels.
- Two board certified neuroradiologists will conduct an initial training session determining allowed contrast filling over the phases.

- Following a washout period of a minimum of two weeks, the neuroradiologists will independently re-review all images and determine a binary outcome of cessation of blood flow compatible with brain death in the same manner as the four vessel angiography is evaluated.
- After an additional wash out period of a minimum of four weeks the images will be independently re-reviewed.
- Following the two reading sessions inter- and intrarater agreements will be determined and comparison to gold standard test will be performed.

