#### **Exclusion Criteria:**

- Examination too risky with regard to circulatory or respiratory instability or equivalent, as assessed by clinically responsible physician.
- Ongoing treatment with extracorporeal membrane oxygenation (ECMO).

As exclusion criterion, we specify treatment with extracorporeal membrane oxygenation (ECMO), since such treatment makes contrast bolus propagation in the pulmonary and systemic circulation difficult to predict, including cerebral vessels.

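### The CT validity check is not linked to the reading: a scan with failed contrast filling has no result category and could be scored as ceased circulation or dropped without trace

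*Protocol*

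**What the plan says.** In the protocol, section 3.6 (Processing of Computed Tomography Angiography) opens with a validity test: the whole series is reviewed, "confirming that it meets the requirements for contrast filling of extracranial vessels". The section neither states those requirements nor gives a consequence for a series that does not meet them.

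After a training session and a washout, "the neuroradiologists will independently re-review all images and determine a binary outcome of cessation of blood flow". A second reading follows: "After an additional wash out period of a minimum of four weeks the images will be independently re-reviewed". Neither reading offers a third category, and neither is said to be limited to series that passed the check.

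Two other parts of section 3.6 bear on this. Under Patient Recruitment, "The computed tomography examination is performed on one occasion". Under Computed Tomography Angiography, after one series without contrast, "the following three examinations constitutes a multiphase examination of the same contrast bolus".

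Section 3.7 excludes ECMO because it "makes contrast bolus propagation in the pulmonary and systemic circulation difficult to predict". The statistical analyses in section 3.6 and the planned analyses in section 3.10 name sensitivity, specificity, predictive values and reader reliability. They give no rule for which scans enter.

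**The concern.** In this test the positive sign is an absence: no contrast inside the skull. Contrast that never arrives properly can produce the same picture as arrested circulation. The extracranial check exists to tell the two apart, but the protocol does not connect its result to the reading form or to the accuracy table.

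The stakes follow from the scientific question in section 1, whether CT can replace four-vessel angiography. A CT that cannot be interpreted has not confirmed cessation, so it has not replaced angiography in that patient. If it is read as ceased in a patient with flow, it is a false positive. The Background (section 2) reports the view that avoiding this error matters far more than sensitivity. If it is read as ceased in a patient with true arrest, CT gets credit for a result it did not produce. If it leaves the denominator, the failure disappears from the estimate.

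The ECMO exclusion shows that the protocol recognises the mechanism. Other patients with compromised circulation remain eligible unless the responsible physician judges the examination too risky. The case report form in section 3.8 records vasopressors and inotropes.

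**Working it through.** The protocol gives no figure on this point. Its sample sizes (about 50 locally, 200 more nationally, about 250 in all) are neither disputed nor changed.

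**Reading the text**

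1. The validity check has no stated consequence.
2. The reading is two-way and covers all images.
3. CT is done once, and all three contrast phases share one bolus. One poor bolus can therefore affect every phase, and the text provides no second examination.
4. A failed scan must then get one of two verdicts or be left out. The text does not say which.

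**Sensitivity, one worked case.** All inputs are assumed; only the total of about 50 comes from the protocol (section 3.3). Take 45 patients with arrest and 5 with flow. Among the 45, 3 scans fail, and 36 of the 42 valid scans are read as ceased.

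- Failed scans read as ceased: (36 + 3)/45 = 86.7%
- Failed scans dropped: 36/42 = 85.7%
- Failed scans counted as not confirmed: 36/45 = 80.0%

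**Sensitivity over a range.** Let *s* be sensitivity among valid scans and *f* the failure rate. The three results are *s*(1 − *f*) + *f*, *s*, and *s*(1 − *f*). Take *s* = 85%, the pooled four-point figure in the Background. That figure was measured against clinical diagnosis, so it is only a convenient value here. The values of *f* are assumed.

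| *f* | Read as ceased | Dropped | Not confirmed |
|---|---|---|---|
| 2% | 85.3% | 85.0% | 83.3% |
| 5% | 85.8% | 85.0% | 80.8% |
| 10% | 86.5% | 85.0% | 76.5% |

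**Specificity.** Assume no other false positives. One failed scan read as ceased gives 4/5 = 80% with 5 patients with flow, or 9/10 = 90% with 10. If every failed scan is read as ceased, the chance of at least one such false positive is 1 − (1 − *f*)^n, where n is the number of patients with flow.

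- n = 5: 10%, 23% and 41% for *f* = 2%, 5% and 10%
- n = 10: 18%, 40% and 65%

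**Checking the remedy on specificity.** Counting non-diagnostic scans as not confirmed makes a failed scan in a patient with flow a true negative. Suppose there are 5 patients with flow, 1 failed scan, and 1 false positive among the 4 valid scans. Specificity is 3/4 = 75% on valid scans and 4/5 = 80% on all patients. The all-patients figure alone would therefore credit CT with a result it did not earn.

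**The case against.** A validity test placed before any reading is naturally understood as a gate, and the later instruction may mean all images from valid examinations. A reader might infer that the protocol directs failed scans to be scored as ceased. It does not say so, and that reading is not supported. This objection stands: the defect is an open gap, not a wrong rule.

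A reader might also infer that either way of handling a failed scan favours CT. That holds only for sensitivity. A failed scan read as ceased when flow is present lowers specificity, so it counts against CT on the measure given most weight in the Background.

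There are safeguards. Phase timing starts when enough contrast reaches the aortic arch, three phases allow later looks, a series without contrast serves as reference, and unstable patients can be excluded. These narrow the risk. They do not ensure filling of the vessels in the head, and the validity check itself presupposes that failures occur.

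The filling requirements may be set out in the prespecified examination protocol, and the analysis set in a statistical analysis plan; neither is shown. Their absence is not the point. The check, the two-way scale and the scope of the reading are fixed in this document and do not fit together. If the form has no third category, a later analysis plan cannot recover a reader's judgement that a scan was non-diagnostic.

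Finally, the failure rates are assumed and the local study is described as hypothesis-generating. In the worked case, the 95% Wilson interval for 36/45 is about 66% to 89%, which contains all three sensitivity estimates. That is fair as to size. But the difference between handling rules is systematic, and more patients would not remove it.

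**Conclusion.** The concern holds as a gap in the reading procedure. As written, a scan with failed filling could be scored as ceased circulation or dropped without record, and the protocol does not say which. It does not show that either will happen.

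The size depends on a failure rate and a share of patients with preserved flow that the protocol does not give. In the worked case, the handling rule moves sensitivity between 80.0% and 86.7%. Reading as ceased and dropping differ by only 1 point; the larger gap is to counting failures as not confirmed. A single misread failed scan costs 10 to 20 points of specificity with 5 to 10 patients with flow. With few such patients in a study of about 50, this is worth settling before reading begins.

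**What to change.** In section 3.6 (Processing of Computed Tomography Angiography):

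- State the extracranial filling requirement, or where it is found. Have validity judged and recorded before the intracranial reading and blind to the angiography result.
- Give the reading form three categories: ceased, not ceased, non-diagnostic.
- Keep every examined patient in the sensitivity denominator, with non-diagnostic counted as cessation not confirmed.
- Report specificity among valid scans alongside the all-patients figure, because the latter turns failed scans in patients with flow into true negatives.
- Report the non-diagnostic rate by angiography result, with valid-scans-only sensitivity as secondary.

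The cost is one extra category on the form, a few sentences of protocol text and a slightly lower headline sensitivity. Recruitment and scanning do not change. Whether a failed scan may be repeated is a clinical matter for the investigators.

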## 3 Project Description

### 3.1 Overall purpose and conditions of the project

We intend to establish and evaluate a new, robust protocol for CT-Angiography to determine total brain infarction. The protocol will methodologically mirror four-vessel angiography, with radiological review of cessation of intradural blood flow incompatible with life. The protocol, which differs significantly from recent recommendations regarding how such a protocol could be designed (15), is intended to be readily available in all modern CT scanners.

The protocol's performance is compared with four-vessel angiography as a confirmatory test for determining cessation of circulation after clinical diagnostics, first in a local, smaller study at Karolinska University Hospital and, in the next step, in a national multicenter study, with the goal of achieving "non-inferiority". Computed tomography angiography is performed according to a clinically standardized protocol, with contrast dose and administration fully in

accordance with CE marking requirements. The study intends to elucidate key aspects of establishing novel ROIs in computed tomography and is to be equated with an interrater assessment study.

In parallel, we also intend to study the patient-near ultrasound modality, Transcranial Doppler (TCD), regarding its predictive and diagnostic performance for this purpose.

The timeline for the pilot study depends on the number of patients cared for in the intensive care units at Karolinska University Hospital, Solna, with suspected total brain infarction requiring confirmation by four-vessel angiography.

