### **3.3 Study Period and Project Plan**

A recent trend towards a larger proportion of donation processes going to DCD (Donation after Circulatory Death) carries the risk of reducing the number of potential research subjects for assessment. We need to consult with next of kin in a challenging situation, which can further affect the recruitment of research subjects. Over the past few years, approximately 15 four-vessel angiographies have been performed annually in our hospital. We believe that a sufficient study basis for statistical comparison of diagnostic performance in a local pilot study can be achieved with approximately 50 patients, during a timeframe of three years. Upon a favorable outcome of this pilot study, we intend to move the project into a second phase, in which the corresponding question is studied within the framework of a national multicenter study with far more patients, providing a stronger statistical foundation.

**Local study:** Patient inclusion is planned from December 2025, or as soon as the ethical application allows. Patient inclusion is planned to continue through December 2028, given an annual decline in the number of examinations. The goal is to recruit approximately 15 patients each year, totaling approximately 50 examinations. An interim analysis is planned after approximately eight examined research subjects, to inform decision-making regarding the reduction and selection of the number and/or phases (image sequences) to be included in the final protocol.

**National multicenter study:** Study start is planned preliminarily for May 2029 and will continue until May 2032 with an ambition to recruit a total of 200 additional patients.

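### The CT readers set the filling rule and then score all images, with no stated masking to four-vessel angiography and no commitment to keep the rule fixed

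*Protocol*

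**What the plan says.** Section 3.6, under Processing of Computed Tomography Angiography, gives this sequence. First: "Two board certified neuroradiologists will conduct an initial training session determining allowed contrast filling over the phases". After at least two weeks, "the neuroradiologists will independently re-review all images and determine a binary outcome of cessation of blood flow", judged as four-vessel angiography is judged. After at least four more weeks the images are read again. Then: "Following the two reading sessions inter- and intrarater agreements will be determined and comparison to gold standard test will be performed".

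Masking appears in the same section under Patient Recruitment: "Images/data/results of computed tomography examination are blinded for the responsible neuroradiologist to avoid bias". The transcranial Doppler (TCD) result is likewise withheld from the responsible neuroradiologist. The protocol contains no other masking statement.

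Section 3.3 plans an interim analysis after about eight subjects, "to inform decision-making regarding the reduction and selection of the number and/or phases (image sequences) to be included in the final protocol".

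Two statements bear on the weight of the point. Section 3.1 says that the study "is to be equated with an interrater assessment study". Section 3.5 says: "The first local study is hypothesis-generating and motivates a subsequent national multicenter study for validation".

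**The concern.** Three features of the reading design act together.

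- **Overlap.** The readers see images again, all of them, after a washout that follows training. The natural inference is that study images were used in training, so that the cases which shaped the rule are scored with it.
- **One-way masking.** The protocol recognises that knowing one test can colour the reading of the other, and it guards the angiography side. It does not guard the CT side, either while the rule is set or while images are scored.
- **A rule that may move.** The allowed filling is defined across the phases, yet the interim analysis may drop or select phases. The order of these two steps is not given, and nothing says the rule is then held constant.

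Agreement is a core output. It may look better than it would in new cases if two readers calibrate together on cases they later score. Sensitivity and specificity may be optimistic if the angiography result is known when the rule is set or the images are read. The Background ranks specificity, meaning no false declaration of ceased circulation, above sensitivity, and the local result is the basis for moving to the multicentre study.

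**Working it through.** The protocol gives no figure to reproduce here, so the check is first textual and then a bound.

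**Text.**
- Order: the rule comes before scored reading. That much is fixed.
- Which images set the rule: not stated. Training on all study images fits the text; training on a subset fits it too.
- Masking of CT readers: not stated. The word describing the readings as independent most naturally separates the readers, or the readings, from each other. Comparing with the reference after both sessions fits masked reading but does not require it.
- Prespecification: the word is applied to the examination protocol, that is, image acquisition. It is not applied to the reading rule.

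**Ceiling on optimism.** Let f be the share of scored cases that set the rule and p the true value. If every rule-setting case then came out concordant, optimism is at most f × (1 − p). This takes the same f among reference-positive cases as overall.

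Inputs: about 50 patients (section 3.3). The sensitivities are from the Background: 75% against four-vessel angiography, 85% against clinical diagnosis, and 97% against a nuclear perfusion test. The figure of 8 rule-setting cases is an assumed example, borrowed from the interim size in section 3.3; nothing links it to the training session.

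| True sensitivity | f = 8/50 = 0.16 | f = 50/50 = 1 |
|---|---|---|
| 75% | 0.16 × 0.25 = 4.0 points | 25 points |
| 85% | 0.16 × 0.15 = 2.4 points | 15 points |
| 97% | 0.16 × 0.03 = 0.5 points | 3 points |

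For percent agreement, with true values of 80% and 90% assumed, the same formula gives 3.2 and 1.6 points for 8 of 50, and 20 and 10 points for all 50.

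The sensitivity rows apply only if the angiography result is known to the readers. No figure is given for specificity, because the protocol does not give the number of patients with persisting flow.

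**Precision lost by leaving out 8 of 50.** The Wald 95% half-width is 1.96 × √(p(1 − p)/n), with all cases taken as reference-positive.
- p = 0.85: n = 50 gives 9.9 points; n = 42 gives 10.8.
- p = 0.75: n = 50 gives 12.0 points; n = 42 gives 13.1.
- Percent agreement at 0.90: 8.3 points becomes 9.1.

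**The case against.** The strongest reply is that developing a rule is what a pilot is for. The local study is declared hypothesis-generating, a multicentre study with 200 additional patients follows for validation, and training readers together before an agreement study is ordinary practice. This stands, and it lowers the harm. It does not remove it, because the local study still reports accuracy and agreement and those results decide whether the next phase begins.

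The protocol also has real safeguards: independent readings, two washouts, and a reading standard borrowed from angiography. The washouts limit recall, but they do not undo a rule fitted to the same cases.

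A written lock and a list of training cases may sit in an analysis plan or reading manual that is not shown, so their absence from the protocol is not itself the finding. The finding is that section 3.6 regulates the reading sequence and the masking, and does so in a way that leaves one side open.

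A reader might also infer more than the text supports:
- *That the rule is set during or after scoring.* Section 3.6 places it before.
- *That scored and rule-setting images are stated to overlap.* This is inferred. Seeing images again may refer in part to the validity check of the whole series.
- *That the readers will know the angiography result.* The protocol is silent. Storing both examinations in one hospital archive is weak evidence, and so is the lack of a statement that readers and operators are different people.
- *That the damage could never be repaired.* The images are archived, so other masked readers could read them again later under a fixed rule.

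**Conclusion.** The point holds as a risk created by the reading design, not as demonstrated bias. Followed as written, section 3.6 lets rule-setting cases enter the agreement and accuracy estimates, leaves the CT readers unmasked to the reference, and does not commit to an unchanged rule when the interim analysis may alter the phases.

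The actual size cannot be derived from the protocol. The ceilings run from about half a point to 4 points for sensitivity if 8 of 50 cases set the rule, and from 3 to 25 points if all 50 did. They assume that every rule-setting case turns out concordant and, for sensitivity, that angiography is known. Their use is to show that the number of rule-setting cases matters far more than anything else in the calculation. The change should be made before the readings begin. Confidence is medium, because the overlap is an inference and the masking gap is a silence.

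**What to change.** In section 3.6:

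1. State that the CT readers are masked to four-vessel angiography, TCD and outcome, including any interim comparison, during training and both reading sessions. Preferably choose readers who did not perform the study angiographies.
2. Set the rule on a small, identified subset of early cases, after the interim phase selection, and keep it unchanged for all scored readings.
3. Report accuracy and agreement for all patients and again with the rule-setting cases excluded.

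The cost is protocol wording and one extra, slightly less precise analysis, about one point wider in half-width if 8 of 50 cases are left out. The all-patient result is kept.

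Three limits should be accepted knowingly. If a reader did perform the angiography in a case, barring that reader removes the case from interrater agreement, which is why choosing other readers is better than a case-by-case bar. If all images set the rule, exclusion leaves nothing to analyse, so the subset must be named first. A small subset may also contain no patient with persisting flow: if 5 to 10 of 50 had flow (assumed), eight cases drawn at random would include none with a chance of C(45,8)/C(50,8) = 40% down to C(40,8)/C(50,8) = 14%.
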